4.4 Exploratory Endpoints

1. Pain Relief at 15, 30, 45, 60, and 90 minutes, 3, 4, 6, 8, 24, and 48 hours post-dose will be assessed using the number of subjects that report a pain level of moderate or severe at baseline and then report a pain level of none or mild at the timepoint of interest.
2. Pain freedom at 3, 4, 6, 8, 24, and 48 hours post-dose will be assessed using the number of evaluable subjects that report no pain at the timepoint of interest.
3. Freedom from MBS at 3, 4, 6, 8, 24, and 48 hours post-dose will be assessed using the number of evaluable subjects that report the absence of their MBS at the timepoint of interest.
4. The proportion of subjects able to function normally, at all post-dose timepoints except 2 hours, will be assessed using the number of subjects that self-report as “normal” on the FDS in the subset of subjects that report any level of disability just prior to taking study medication.
5. Freedom from phonophobia at all post-dose time points will be assessed using the number of evaluable subjects that report the absence of their phonophobia at the timepoint of interest.
6. Freedom from photophobia at all post-dose time points will be assessed using the number of evaluable subjects that report the absence of their photophobia at the timepoint of interest.
7. Freedom from nausea at all post-dose time points will be assessed using the number of evaluable subjects that report the absence of their nausea at the timepoint of interest.
8. Sustained pain relief from 2 to 24 hours, will be assessed using the number of subjects that report a pain level of none or mild through the time period of interest.
9. Sustained pain relief from 2 to 48 hours, will be assessed using the number of subjects that report a pain level of none or mild through the time period of interest.
10. Freedom from MBS from 2 to 24 hours post-dose will be assessed using the number of evaluable subjects that report the absence of their MBS through the time period of interest.
11. Freedom from MBS from 2 to 48 hours post-dose will be assessed using the number of evaluable subjects that report the absence of their MBS through the time period of interest.
12. The proportion of subjects able to function normally from 2 to 24 hours post-dose, will be assessed using the number of subjects that self-report as “normal” on the FDS through the time period of interest.

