13. The proportion of subjects able to function normally from 2 to 48 hours post-dose, will be assessed using the number of subjects that self-report as “normal” on the FDS through the time period of interest.
14. Time to rescue medication use up to 24 hours pose-dose
15. Time to first report of pain freedom up to 8 hours pose-dose
16. Time to first report of freedom from MBS up to 8 hours pose-dose
17. Time to first report of pain relief up to 8 hours pose-dose
18. Time to first report of absence of nausea up to 8 hours pose-dose
19. Time to first report of absence of photophobia up to 8 hours pose-dose
20. Time to first report of absence of phonophobia up to 8 hours pose-dose
21. Time to first report of return to normal functioning up to 8 hours post dose

5 Sample Size

If roughly 85% of the 715 subjects randomized to each treatment arm have a migraine in the allotted time period, there will be approximately 600 treated subjects per group.

Based on data from studies BHV3000-301 and BHV3000-302, 600 treated subjects provides 95% power to detect a difference between rimegepant and placebo on the subject’s self-reported most bothersome symptom. Also, 600 subjects provides 95% power to detect a difference in freedom from pain at 2 hours. Having at 95% power on each co-primary endpoint provides roughly 90% power to detect a difference on both endpoints jointly.

6 Analysis Sets

The following analysis sets will be evaluated and used for presentation and analysis of the data:

- Enrolled subjects: Subjects who sign an informed consent form and are assigned a subject identification number.
- Randomized subjects: Enrolled subjects who receive a randomization treatment assignment from the IWRS (rimegepant or placebo).
- Treated subjects: Enrolled subjects who take study therapy (rimegepant or placebo).
- Modified Intent to Treat (mITT) subjects: randomized subjects that take study therapy, have a migraine of moderate or severe intensity at the time of treatment, and provide at least one post-treatment efficacy data point.

No separate per protocol analysis set is defined for this study. There will not be any per protocol analysis conducted for this study.

7 Statistical Methods

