7.6.2.2 Function Normally at 2 Hours Post-Dose

Subjects rate the level of disability they perceive as a result of their migraine in performing normal actions using a 4-point scale: Normal Function, Mild Impairment, Severe Impairment, or Required Bedrest. The proportion of mITT subjects who report “abnormal” at baseline and have a response of “normal” at the 2 hours post-dose will be evaluated using the same methodology described in section [7.6.1.1](#).

Subjects with missing data at 2 hours post-dose will be imputed as failures (NC=F). Subjects that use rescue medication prior to reporting function normality at 2 hours will be classified as failures (RM=F).

The information from the 4-point scale will be directly summarized as follows:

A table showing descriptive statistics for the 4-point scale, which includes the number and percentage of subjects reporting each of the 4 disability levels at the specified timepoint post-dose, and the percentage of subjects with missing data, for each treatment group, using the observed data. The table will include exact (Clopper-Pearson) 95% CIs for each percentage.

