7.6.4 Exploratory Efficacy Analyses

7.6.4.1 Binary Exploratory Endpoints

The binary exploratory endpoints will be evaluated using the same methodology described in section 7.6.1.1. The definitions of the binary exploratory endpoints are listed in the table 1 below.

Table 1 Definitions of the Binary Exploratory Endpoints

| Endpoints | Definition of Success | Missing Data or Rescue Medication Handling |
|---|--|--|
| Pain Relief at 15, 30, 45, 60, and 90 minutes, 3, 4, 6, 8, 24, and 48 hours post-dose | Report a pain level of none or mild (responses of 0 or 1 on the 4-point Likert scale) at specified post-dose time point | NC=F; RM=F |
| Pain freedom at 3, 4, 6, 8, 24, and 48 hours post-dose | Report a pain level of none (responses of 0 on the 4-point Likert scale) at specified post-dose time point | NC=F; RM=F |
| Freedom from MBS at 3, 4, 6, 8, 24, and 48 hours post-dose | Report an absence of their MBS (reported at migraine onset) at specified post-dose time point | NC=F; RM=F; IP=F |
| Function normally at all post-dose timepoints except 2 hours | Subjects who report “abnormal” at baseline and have a response of “normal” at specified post-dose time point | NC=F; RM=F |
| Freedom from phonophobia at all post-dose time points | Subject who have phonophobia present at baseline and have absence of phonophobia at specified post-dose time point | NC=F; RM=F |
| Freedom from photophobia at all post-dose time points | Subject who have photophobia present at baseline and have absence of photophobia at specified post-dose time point | NC=F; RM=F |
| Freedom from nausea at all post-dose time points | Subjects who have nausea present at baseline and have absence of nausea at specified post-dose time point | NC=F; RM=F |
| Sustained pain relief from 2 to 24 hours | Subjects that experience no or mild headache pain (response of 0 or 1 on Likert scale) at all time points from 2 through 24 hours post-dose; Subjects with missing pain scores at 1 or fewer | NC1=F; RM=F |

| Endpoints | Definition of Success | Missing Data or Rescue Medication Handling |
|---|---|--|
| | time points, given that they have responses of no or mild pain (response of 0 or 1 on 4-point Likert scale) at all other time points including the 2 and 24 hour post-dose time points, will be considered as successes. | |

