| Sustained pain relief from 2 to 48 hours | Subjects that experience no or mild headache pain (response of 0 or 1 on Likert scale) at all time points from 2 through 48 hours post-dose; Subjects with missing pain scores at 1 or fewer time points, given that they have responses of no or mild pain (response of 0 or 1 on 4-point Likert scale) at all other time points including the 2, 24 and 48 hour post-dose time points, will be considered as successes. | NC1=F; RM=F |
| Freedom from MBS from 2 to 24 hours post-dose | Subjects that experience freedom from their MBS at all time points from 2 through 24 hours post-dose; Subjects with missing MBS data at 1 or fewer time points, given that they have responses of freedom from MBS at all other time points including the 2 and 24 hour post-dose time points will be considered as successes. | NC1=F; RM=F; IP=F |
| Freedom from MBS from 2 to 48 hours post-dose | Subjects that experience freedom from their MBS at all time points from 2 through 48 hours post-dose; Subjects with missing MBS data at 1 or fewer time points, given that they have responses of freedom from MBS at all other time points including the 2, 24, and 48 hour post-dose time points will be considered as successes. | NC1=F; RM=F; IP=F |

| Endpoints | Definition of Success | Missing Data or Rescue Medication Handling |
|--|--|--|
| Function normally from 2 to 24 hours post-dose | Subjects that experience normal functioning on the FDS at all time points from 2 through 24 hours post-dose. Subjects with missing FDS scores at 1 or fewer time points, given that they have responses of normal at all other time points including the 2 and 24 hour post-dose time points will be considered as successes. | NC1=F; RM=F |
| Function normally from 2 to 48 hours post-dose | Subjects that experience normal functioning on the FDS at all time points from 2 through 24 hours post-dose. Subjects with missing FDS scores at 1 or fewer time points, given that they have responses of normal at all other time points including the 2, 24 and 48 hours post-dose time points will be considered as successes. | NC1=F; RM=F |

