7.6.4.2 Time to Event Endpoints

Time to First Use of Rescue Medication

Kaplan-Meier (K-M) plots will be created for the time to first use of rescue medication. The K-M plot will cover the 24 hour period after dosing. Subjects who did not take rescue medication within 24 hours of dosing will be censored at 24 hours and 1 minute. Regardless of pain or MBS response, subjects are considered at risk until the first use of rescue medication, loss to follow-up (last contact date), or the end of the 24-hour period, whichever comes first. The analysis population consists of mITT subjects.

Two tables will be created to support the plot. The first table presents the median time to rescue medication along with 95% CIs calculated using the method of Brookmeyer and Crowley and the log-rank p-value. The second table presents the number of subjects at risk, with an event, censored, and the survival probability estimate (with 95% CI) from the K-M product limit method for each period (e.g., 0-<2 hours, 2-<4 hours, ..., 20-<22 hours, 22-24 hours) by treatment group.

Time to First Report of Pain Freedom, Pain Relief or Absence of Various Symptoms

For each of the following events, two sets of K-M plots and tables will be created:

- Time to first report of pain freedom up to 8 hours pose-dose
- Time to first report of freedom from MBS up to 8 hours pose-dose
- Time to first report of pain relief up to 8 hours pose-dose
- Time to first report of absence of nausea up to 8 hours pose-dose
- Time to first report of absence of photophobia up to 8 hours pose-dose
- Time to first report of absence of phonophobia up to 8 hours pose-dose
- Time to first report of return to normal functioning up to 8 hours post dose

For both sets of analyses, the analysis population for pain freedom, pain relief and MBS is the set of mITT subjects. The analysis population for nausea, phonophobia, and photophobia is the subset of mITT subjects that reported the symptom as present at the onset of their study migraine. The analysis population for functional disability is the subset of mITT subjects that reported abnormal functioning at the onset of their study migraine.

a) Actual Time for Event of Interest

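### The exploratory sustained normal-function endpoints omit the baseline-impaired restriction that the SAP applies to every other functional-disability endpoint

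*SAP*

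**What the plan says.** Two exploratory endpoints in SAP 4.4 concern sustained function. Item 12 reads "The proportion of subjects able to function normally from 2 to 24 hours post-dose, will be assessed using the number of subjects" who self-report as normal on the Functional Disability Scale (FDS) through the period. Item 13 is the same for the longer window: "The proportion of subjects able to function normally from 2 to 48 hours post-dose, will be assessed using the number of subjects". Neither mentions function before dosing.

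Table 1 in SAP 7.6.4.1 gives the operational rule. Success is "Subjects that experience normal functioning on the FDS at all time points from 2 through 24 hours post-dose", with one missing score tolerated outside the critical time points. The handling codes are NC1=F and RM=F. There is again no baseline condition. SAP 7.6 makes mITT the default efficacy population. The mITT definition in SAP section 6 requires a moderate or severe migraine at treatment but says nothing about function.

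The other functional endpoints are restricted:

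- **2 h key secondary.** SAP 4.2.1 item 2 uses the subset with any disability just before dosing. SAP 7.6.2.2 counts "The proportion of mITT subjects who report “abnormal” at baseline" and normal at 2 h.
- **Other single time points.** SAP 4.4 item 4 is assessed "in the subset of subjects that report any level of disability just prior to taking study medication". The Table 1 row is "Subjects who report “abnormal” at baseline and have a response of “normal” at specified post-dose time point".
- **Time to normal functioning.** SAP 4.4 item 21 is a one-line entry without a restriction, but SAP 7.6.4.2 supplies it: "The analysis population for functional disability is the subset of mITT subjects that reported abnormal functioning at the onset of their study migraine".

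Protocol 2.3 lists the two sustained objectives without a restriction, and Protocol 3.3 leaves exploratory endpoint definitions to the SAP. No reason is given for treating the sustained versions differently.

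**The concern.** A sustained response from 2 h is normally read as a 2 h response that lasts. That reading requires every sustained success to be a 2 h success as well. Here it need not be. A subject who is normal at dosing and stays normal meets the sustained definition but fails the 2 h numerator, which requires abnormal function at baseline.

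Two things are at stake. The sustained rates mix recovery of function with preservation of function that was never lost. And the sustained result cannot be set directly beside the 2 h key secondary, because the two describe different sets of subjects.

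The omission looks like an oversight. Table 1 does add baseline conditions where they matter. Its phonophobia, photophobia and nausea rows require the symptom to be present at baseline, although the endpoint list in SAP 4.4 does not state this. The sustained-function rows received no such condition.

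**Working it through.** **Step 1: can a subject be unimpaired at dosing?** Yes. The FDS has four levels, one of them normal function (SAP 7.6.2.2). mITT entry depends on pain intensity, not function. The restriction in SAP 4.2.1 item 2 itself presupposes that some subjects are normal at dosing.

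**Step 2: follow one such subject through the definitions.** Take an mITT subject who is normal at dosing, normal at every rating from 2 h on, and uses no rescue medication.

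| Endpoint | Status of this subject |
|---|---|
| Normal function at 2 h (4.2.1 item 2; 7.6.2.2) | Not a success; outside the subset |
| Other single time points (4.4 item 4; Table 1) | Not a success; outside the subset |
| Time to normal functioning (7.6.4.2) | Not in the analysis population |
| Sustained 2-24 h and 2-48 h (4.4 items 12-13; Table 1) | Success |

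This holds even if the denominator in 7.6.2.2 is read as all mITT subjects, because its numerator still requires abnormal function at baseline.

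**Step 3: size.** The plan states no figure on this point, so there is none to reproduce. Let q be the share normal at dosing. In each arm:

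unrestricted rate = (1 − q) × rate in impaired + q × rate in unimpaired.

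The documents give none of these inputs, so all values below are assumptions.

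*Scenario A.* Sustained success 25% v 15% (rimegepant v placebo) in impaired subjects and 60% v 55% in unimpaired subjects.

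| q | Rimegepant | Placebo | Difference |
|---|---|---|---|
| 0 | 25.0% | 15.0% | 10.0 |
| 5% | 0.95×25 + 0.05×60 = 26.75% | 0.95×15 + 0.05×55 = 17.0% | 9.75 |
| 10% | 0.90×25 + 0.10×60 = 28.5% | 0.90×15 + 0.10×55 = 19.0% | 9.5 |
| 15% | 0.85×25 + 0.15×60 = 30.25% | 0.85×15 + 0.15×55 = 21.0% | 9.25 |

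Both arms rise: placebo by 2 to 6 points, rimegepant by 1.75 to 5.25.

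*Scenario B.* 16% v 10% in impaired subjects and an equal 60% in unimpaired subjects, with the plan's target of 600 per arm. The difference is then multiplied by (1 − q). Power is the two-sided 0.05 test of two proportions with pooled variance under the null. At 600 per arm this method returns 95.1% for 14% v 22% and 64.6% for 14% v 19%, matching Table 4 of Protocol Appendix IV.

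| q | Unrestricted rates | Difference | Power, unrestricted | Power, impaired only (n per arm) | Placebo successes from unimpaired |
|---|---|---|---|---|---|
| 5% | 18.2% v 12.5% | 5.7 | 78% | 86% (570) | 0.05×60/12.5 = 24% |
| 10% | 20.4% v 15.0% | 5.4 | 69% | 84% (540) | 0.10×60/15.0 = 40% |
| 20% | 24.8% v 20.0% | 4.8 | 51% | 79% (480) | 0.20×60/20.0 = 60% |

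*No dilution.* If the unimpaired difference is also 10 points (65% v 55%, other inputs as in A), then q = 10% gives 0.90×25 + 0.10×65 = 29.0% v 19.0%. The difference stays at 10.0 points, though both rates still rise.

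**The case against.** The best defence is that an all-mITT proportion functioning normally throughout 2-24 h is a legitimate estimand that keeps the full analysis set. The other sustained endpoints (SAP 4.4 items 8-11) carry no baseline-subset clause either. Table 1 defines success rather than a denominator, and the table shells named in SAP section 9, which are not available here, may settle it. Subject-level efficacy data are listed, so a restricted rate could be derived later. Both endpoints are exploratory.

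Part of this stands. The all-mITT estimand is valid if stated and justified, no confirmatory inference depends on it, and a restricted rate needs no new data. The analogy with items 8-11 does not stand. mITT entry guarantees moderate or severe pain, and SAP 7.6.1.2 and Table 1 count an unreported MBS as failure. Nothing guarantees impaired function. Shells that cannot be seen do not replace a definition in the SAP, and deriving the restricted rate after unblinding means choosing the denominator with the results known.

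A reader might also infer three stronger things that the documents do not support:

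- **That every subject normal at dosing counts as a success.** NC1=F and RM=F still apply, and a subject in a moderate or severe attack may become impaired or take rescue medication.
- **That the difference is necessarily diluted.** This holds only if the treatment difference is smaller in unimpaired subjects. Staying normal during an attack may also respond to treatment.
- **That the omission favours rimegepant.** Function at dosing is recorded before treatment in randomised arms, so no such bias is expected.

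**Conclusion.** The inconsistency is real and minor. Followed as written, items 12-13 and their Table 1 rows admit subjects whom every other functional endpoint leaves out, so the sustained result is not a continuation of the 2 h key secondary and is not directly comparable with it.

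The sustained rates are raised in both arms, given only that unimpaired subjects stay normal more often than impaired subjects become and stay normal. The amount cannot be determined from the documents, and the figures in both scenarios rest wholly on assumed inputs. In Scenario A the rates move more than the difference does. Scenario B, with no treatment effect in unimpaired subjects, shows a larger loss.

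Both endpoints lie outside the co-primaries and the Hochberg family of five key secondaries, so no confirmatory conclusion changes.

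**What to change.** Before unblinding, amend SAP 4.4 items 12 and 13 and the two sustained-function rows of Table 1 in 7.6.4.1. Numerator and denominator should both be restricted to mITT subjects reporting any functional disability just before dosing, as in item 4. Use the same FDS record as the 2 h analysis in 7.6.2.2.

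If the all-mITT proportion is also of interest, keep it as a labelled supplementary tabulation. The same edit can correct the 2-48 h row of Table 1, whose success definition stops at 24 hours although it requires the 48 h rating.

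The cost is one clause in each of four places, plus any matching change to the table shells. Baseline FDS is already collected at migraine onset (Protocol Table 1), so no new data are needed. The price is a somewhat smaller denominator: about 540 rather than 600 per arm if 10% were normal at dosing.

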7.1 General Statistical Considerations

All relevant data from all subjects entered into the database will be included in subject data listings. Unless specified otherwise, by-subject listings will be sorted by site, subject ID, and additional variables such as time points, as applicable. Listings will display site-subject ID and as randomized treatment group (as-treated treatment group for safety).

Tabulations will be produced for appropriate demographic, baseline, efficacy, and other parameters by as-randomized treatment group (BHV3000, Placebo) and overall, unless specified otherwise. For safety analyses, tabulations will be produced by as-treated treatment group (BHV3000, Placebo) and overall, unless specified otherwise. For categorical variables, summary tabulations of the number and percentage of subjects within each category will be presented. If applicable, a category for missing data will also be presented. For continuous variables, descriptive statistics (e.g., n, mean, median, standard deviation (SD), minimum, and maximum) will be presented. The minimum and maximum will be presented with the same precision as the data. The mean and median will be presented with the precision of the data + 1 decimal place. The SD will be presented with the precision of the data + 2 decimal places. In general, the maximum number of decimal places reported should be 4 for any summary statistics.

Formal statistical hypothesis testing and summary statistics will be presented, as well as confidence intervals (CIs) on selected endpoints, as described in the sections below.

Unscheduled or repeat assessments will not be included in summary tables unless specified otherwise, but will be included in listings.

For efficacy analyses, baseline is considered as the assessment at the onset of the treated migraine. Otherwise, baseline is the last non-missing assessment before or on the randomization date.

All statistical computations and construction of tables, listing and figures will be performed using SAS® Version 9.4 or later.

7.2 Adjusting of Covariates

The randomization is stratified by the use of prophylactic migraine medication (yes or no) and country (China and Korea). Hence, most analyses are stratified by the use of prophylactic medication and country.

